11.3.1. Efficacy Analyses

Demographic characteristics (age, sex, race) of each study group will be tabulated.

The mean age (plus range and standard deviation) by sex of the enrolled participants, as a whole and per group, will be calculated.

The primary analysis will be performed using the modified Intention-to-Treat population. If the participant is not SARS-CoV-2 positive by laboratory test, their infection time will be censored at the last negative swab test date at or before the Day 14 swab. A logistic model stratified by site and accounting for within-household correlation will be used to assess the efficacy of the HCQ group compared to control. To aid understanding of the results from the logistic model, cumulative incidence Kaplan-Meier curves of time to infection will be presented by site and treatment arm.

Subgroup Analyses

All subgroup analyses will be pre-specified in the Statistical Analysis Plan. Any further subgroups will be considered *ad hoc*.

Missing Data

Due to the design of the study and retention activities, we expect to be able to categorize all infections as either incident or prevalent at baseline. However, in the unlikely event of a missing test result, the missing data will be imputed.

Additional analyses will be described in the Statistical Analysis Plan finalized before database lock.

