3. GENERAL DATA ANALYSIS CONSIDERATIONS

3.1. ANALYSIS SET(S)

This section describes the cohorts for the primary, secondary and exploratory analyses described in this document.

Intention to Treat (ITT) Cohort: The ITT Cohort includes all contacts enrolled into the study.

Modified Intention to Treat (mITT) Cohort: Contacts who are SARS-CoV-2 negative by PCR at the baseline visit.

mITT Sensitivity Cohort: Contacts in the mITT cohort who are SARS-CoV-2 negative by PCR at the day 1-3 visits. Participants who are SARS-CoV-2 negative on two of the three days, without a SARS-CoV-2 positive result, will be included in this cohort.

Seronegative Cohort: If a validated, sensitive and specific assay is available for antibody testing, this cohort will include all mITT cohort participants who are antibody negative at baseline.

Infected Cohort: Contacts who are SARS-CoV-2 positive by PCR at the baseline visit.

PK Cohort: Participants from the DBS Sub-study with at least 1 interpretable PK sample

Household Cohort: All enrolled index cases and their household contacts. Enrolled indexes are enrolled in either the PEP Study or the companion Early Treatment Study.

Index Cohort: All enrolled index cases.

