7.1.1. Primary efficacy analyses

Objective: To estimate the efficacy of HCQ (400 mg orally daily for 3 days then 200 mg orally daily for an additional 11 days, to complete 14 days) to prevent incident SARS-CoV-2 infection, compared to ascorbic acid among contacts of persons with SARS-CoV-2 infection.

Outcome: Polymerase chain reaction (PCR)-confirmed SARS-CoV-2 infection through Day 14

Cohorts: mITT Cohort, Sensitivity Cohort

Definition of Endpoint: An endpoint defining PCR test is defined as one with either concordant results or $Ct \leq 40$ and will be referred to as positive test for this analysis. PCR tests not meeting these criteria will be referred to as negative. A participant will be defined as having reached the endpoint on the midpoint between the days of collection of their first positive result and last negative result (prior to the positive result) in the first 13 days of follow-up. Participants who have confirmed COVID-19 through external evaluation in the first 13 days (e.g. hospital or clinical assessment) will be defined as having reached the endpoint at the midpoint between the last prior negative test and the day of the external diagnosis. Participants who do not reach the endpoint will have their follow-up censored at their last negative RNA test. Any uncertainty in final endpoint determination will be resolved by the blinded Endpoint Adjudication Committee.

Analysis Details:

The primary analysis will be performed on the mITT Cohort. A sensitivity analysis will be performed on the Sensitivity Cohort to account for potential missed infections at day 1.

We will use a Cox Proportional Hazards model with robust standard errors to estimate the hazard ratio and corresponding 95% confidence interval and Wald test statistic. Efficacy will be calculated as 1 minus the hazard ratio (treatment/control) from the treatment coefficient. Robust confidence intervals and p-values will be displayed. Per FDA guidance on prevention studies, the following variables will be included to increase precision: quarantine status, sex, and age of contact.

The number of evaluable participants per arm will be displayed (defined as participants with at least one PCR test result or external diagnosis) by arm with person-days of follow-up and number of endpoints per arm and prevalence of endpoints (number reached endpoint/number evaluable) with a 95% confidence interval calculated using exact binomial confidence intervals.

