7.1.2. Secondary efficacy analyses

Infection by day 28

Objective: To test the efficacy of HCQ (400 mg orally daily for 3 days then 200 mg orally daily for an additional 11 days, to complete 14 days) to prevent incident SARS-CoV-2 infection two weeks after completing therapy, compared to ascorbic acid among contacts of persons with SARS-CoV-2 infection.

Outcome: Polymerase chain reaction (PCR)-confirmed SARS-CoV-2 infection through Day 28

Cohorts: mITT Cohort, Sensitivity Cohorts

Definition of Endpoint: An endpoint defining PCR test is defined as one with either concordant results or $Ct \leq 40$ and will be referred to as positive test for this analysis. PCR tests not meeting these criteria will be referred to as negative. A participant will be defined as having reached the endpoint on the midpoint between the days of collection of their first positive and last negative PCR tests (prior to a positive test). Participants who have confirmed COVID-19 through external evaluation (e.g. hospital or clinical assessment) will be defined as having reached the endpoint at the midpoint between the last negative test (prior to external diagnosis) and the day of the external diagnosis. Participants who do not reach the endpoint will have their follow-up censored at their last negative test. Any uncertainty in final endpoint determination will be resolved by the blinded Endpoint Adjudication Committee.

Analysis Details: The same analytical approaches will be applied as for the primary efficacy analysis, including a primary analysis on the mITT Cohort and a sensitivity analysis on the Sensitivity Cohort.

Duration of shedding

Objective: To test the efficacy of HCQ to shorten the duration of SARS-CoV-2 shedding among those with SARS-CoV-2 infection.

Outcome: SARS-CoV-2 viral shedding by PCR

Cohort(s): mITT Cohort

Definition of Endpoint: For this analysis, a positive PCR test is defined as one where both targets are identified or one target is identified with $Ct \leq 40$.

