7.1.3. Sensitivity efficacy analyses

The following sensitivity analysis will be performed including the one defined in Section 7.1.1.

Objective: To repeat the primary analysis redefining the endpoint to exclude inconclusive tests with Ct>38 from the definition of the endpoint.

Outcome: Polymerase chain reaction (PCR)-confirmed SARS-CoV-2 infection (self-collected samples collected daily Day 1 through Day 14])

Cohorts: mITT Cohort

Definition of Endpoint: A participant will be defined as having the endpoint if at least one of their PCR tests throughout follow-up is positive (both targets are identified or the Ct is <=38) or they develop confirmed COVID-19 through external evaluation (e.g. hospital or clinical assessment).

Analysis Details:

The same analytical approaches will be applied as for the primary efficacy analysis with a positive test now being defined as concordant results (positive) or a Ct <=38. Inconclusive tests will be treated as negative.

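### The per-arm infection proportions get an exact binomial interval that ignores household randomisation, and the evaluable rule, read literally, excludes nobody

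*SAP*

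**What the plan says.** SAP 7.1.1 displays, by arm, the person-days of follow-up, the number of endpoints and the "prevalence of endpoints (number reached endpoint/number evaluable"), the last "with a 95% confidence interval calculated using exact binomial confidence intervals". Evaluable is "defined as participants with at least one PCR test result or external diagnosis". The analysis set is given in SAP 3.1: "Modified Intention to Treat (mITT) Cohort: Contacts who are SARS-CoV-2 negative by PCR at the baseline visit".

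Two later analyses refer back to this section. SAP 7.1.2 (Day 28) states: "The same analytical approaches will be applied as for the primary efficacy analysis, including a primary analysis on the mITT Cohort". SAP 7.1.3 (stricter Ct cut-off) states: "The same analytical approaches will be applied as for the primary efficacy analysis with a positive test now being defined as concordant results".

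On the design, SAP 2.1 and protocol 7.5 randomise by household, and protocol 11.1 analyses individuals. Protocol 11.3.1 asks the primary model to account for within-household correlation, and SAP 2.4 cites that correlation as the reason for moving to 90% power. Protocol 11.3.1 also says that "cumulative incidence Kaplan-Meier curves of time to infection will be presented by site and treatment arm" and that "in the unlikely event of a missing test result, the missing data will be imputed".

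**The concern.** There are two separate points.

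**The interval.** An exact binomial interval assumes independent observations. Contacts in one household share an index case, a dwelling and a treatment arm, so positive correlation is plausible, and the sponsor accepts this elsewhere. The robust standard errors in SAP 7.1.1 belong to the Cox model and do not reach this interval. Read literally, the Day 28 and Ct analyses inherit it.

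**The denominator.** Every mITT member has a negative baseline PCR result, so everyone satisfies the evaluable rule. The Sensitivity Cohort is a subset of mITT, so the same applies there. A participant with only the baseline swab is censored at that swab and adds nothing to the Cox model, but enters the crude proportion as a non-event. The SAP neither carries over nor withdraws the protocol's imputation.

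At stake is the absolute risk that readers will see beside the hazard ratio: its error bars would be too short, and its value could be too low.

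**Working it through.** **Inputs.** From SAP 2.4: 93 events, 10% control attack rate, 50% reduction, 1240 participants negative at baseline. From protocol Table 1: household-size distributions A, B and C. Not in the documents, so assumed: the ICC (0 to 0.5) and the share of mITT members with only a baseline swab (1% to 10%).

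**1. The plan's own figures.** Average risk is (0.10 + 0.05)/2 = 0.075, and 93/0.075 = 1240, as stated. At 1:1 that is 620 per arm, with 0.10 × 620 = 62 and 0.05 × 620 = 31 events; 62 + 31 = 93.

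**2. Interval as planned (Clopper-Pearson).** 62/620: 7.75% to 12.64%. 31/620: 3.42% to 7.02%.

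**3. Allowing for households.** The size-weighted household size is m_eff = Σm²p / Σmp, and the design effect is DE = 1 + (m_eff − 1) × ICC. The adjusted interval is Clopper-Pearson on x/DE out of n/DE. For the control arm:

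| Row | m_eff | DE, ICC 0.1 | CI (width ratio) | DE, ICC 0.3 | CI (width ratio) |
|---|---|---|---|---|---|
| A | 2.47/1.35 = 1.83 | 1.08 | 7.67–12.76% (1.04) | 1.25 | 7.51–12.98% (1.12) |
| B | 2.62/1.40 = 1.87 | 1.09 | 7.66–12.76% (1.04) | 1.26 | 7.49–13.00% (1.13) |
| C | 7.92/2.50 = 3.17 | 1.22 | 7.54–12.94% (1.11) | 1.65 | 7.16–13.49% (1.30) |

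For the HCQ arm at ICC 0.3: row A 3.26–7.30%, row B 3.25–7.32%, row C 3.03–7.72%.

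**4. Coverage of the planned 95% interval.** Household sizes were drawn from Table 1, household risk was beta-distributed, each arm had about 620 participants, and each cell had 20,000 runs (Monte Carlo standard error 0.15 to 0.26 points). At a 10% rate:

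| Row | ICC 0 | 0.05 | 0.1 | 0.2 | 0.3 | 0.5 |
|---|---|---|---|---|---|---|
| A | 95.9% | 95.3% | 94.9% | 93.9% | 92.7% | 90.8% |
| B | 95.9% | 95.0% | 94.9% | 93.9% | 92.8% | 91.0% |
| C | 95.8% | 94.6% | 93.3% | 90.8% | 88.6% | 83.8% |

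At a 5% rate, coverage at ICC 0.3 is 93.6%, 93.7% and 88.7% for rows A, B and C. Exact intervals are slightly conservative, so a small ICC is absorbed. Coverage falls below 95% from an ICC of about 0.05 in row C and about 0.1 in rows A and B.

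**5. A clustered alternative.** With K households in the arm, y_h infections among m_h members of household h, and n participants, the variance is Σ(y_h − m_h p)²/n² × K/(K − 1), with the interval formed on the logit scale. This was simulated with 10,000 runs per setting, for three rows, two rates (10% and 5%) and five ICCs from 0 to 0.3. Coverage was 94.5% to 95.6% in all 30 settings. Mean width relative to the exact interval was 0.97 at ICC 0. At ICC 0.3 it was 1.08 to 1.09 in rows A and B and 1.25 in row C.

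**6. Denominator.** mITT membership implies at least one PCR result, so the evaluable set equals mITT and the rule removes nobody. It could remove someone only if a missing baseline result were imputed as negative, which the SAP does not provide for. If a share f has only the baseline swab, unrelated to infection risk, and nothing is imputed, the displayed rate is p × (1 − f):

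| f | True 10% shown as | True 5% shown as |
|---|---|---|
| 1% | 9.9% | 4.95% |
| 2% | 9.8% | 4.9% |
| 5% | 9.5% | 4.75% |
| 10% | 9.0% | 4.5% |

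**The case against.** The interval is descriptive. Efficacy is tested by the Cox model with robust standard errors, and SAP 8.1 monitors on the robust Wald statistic. This stands, and it caps the importance of the point.

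In rows A and B the loss of coverage is negligible up to an ICC of about 0.1. Coverage near 89% to 91% by an ICC of 0.3 needs the larger households of row C together with an ICC of 0.2 to 0.3, both assumptions. This also stands, but the SAP has no basis for assuming the favourable case.

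A reading of evaluable that excludes nobody makes the external-diagnosis clause idle too, so a post-baseline result was probably meant. That is likely, and this part is then a request to say so. The dilution also concerns only people who miss every follow-up swab. The protocol considers even a missing result unlikely, and at 1% to 2% the shift is 0.1 to 0.2 points against a half-width of (12.64 − 7.75)/2 ≈ 2.4 points. The person-days shown alongside would partly reveal the problem.

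Finally, requiring one post-baseline result still counts someone who stops after Day 2 as a full non-event, and it adds a post-randomisation exclusion. That is correct, and it is why Kaplan-Meier is the preferred remedy.

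**Conclusion.** Both parts hold, and the point is minor. SAP 7.1.1 names a method that ignores the unit of randomisation, and nothing else in the documents corrects it for this interval. For ICCs of 0.1 to 0.3 the interval should be about 4% to 13% wider in rows A and B and 11% to 30% wider in row C, on the design-effect calculation. These sizes rest on an assumed ICC, the hypothetical household distributions in protocol Table 1 and the SAP's expected event counts. The understatement of the proportion depends on the literal evaluable rule, no imputation, and an undocumented share of participants with only a baseline swab. Neither part changes the hazard ratio, its test or the monitoring.

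**What to change.** Report infection by Day 14 in each arm as Kaplan-Meier cumulative incidence with a 95% interval that is clustered on household or bootstrapped over households. The protocol already plans such curves by site and arm, and SAP 7.1.4 already plans Day 14 cumulative incidence with intervals in subgroups, so this adds the arm-level summary and its clustered interval. Kaplan-Meier also handles early loss.

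If the crude proportion is kept, use a cluster-adjusted interval, require at least one post-baseline PCR result or an external diagnosis, and state whether the protocol's imputation applies. Make the same change wherever SAP 7.1.2 and 7.1.3 refer back to the primary analysis.

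As a clarification only, name household as the cluster for the robust standard errors in the final and interim Cox models. Protocol 11.3.1 and SAP 2.4 and 8.1 already imply this.

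The cost is SAP wording and a few lines of code; SAP 6 already lists the number of household members enrolled as contacts. In the simulation the clustered interval is no wider when the ICC is 0, 8% to 9% wider at ICC 0.3 in rows A and B, and 25% wider in row C.

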7.1.2. Secondary efficacy analyses

Infection by day 28

Objective: To test the efficacy of HCQ (400 mg orally daily for 3 days then 200 mg orally daily for an additional 11 days, to complete 14 days) to prevent incident SARS-CoV-2 infection two weeks after completing therapy, compared to ascorbic acid among contacts of persons with SARS-CoV-2 infection.

Outcome: Polymerase chain reaction (PCR)-confirmed SARS-CoV-2 infection through Day 28

Cohorts: mITT Cohort, Sensitivity Cohorts

Definition of Endpoint: An endpoint defining PCR test is defined as one with either concordant results or $Ct \leq 40$ and will be referred to as positive test for this analysis. PCR tests not meeting these criteria will be referred to as negative. A participant will be defined as having reached the endpoint on the midpoint between the days of collection of their first positive and last negative PCR tests (prior to a positive test). Participants who have confirmed COVID-19 through external evaluation (e.g. hospital or clinical assessment) will be defined as having reached the endpoint at the midpoint between the last negative test (prior to external diagnosis) and the day of the external diagnosis. Participants who do not reach the endpoint will have their follow-up censored at their last negative test. Any uncertainty in final endpoint determination will be resolved by the blinded Endpoint Adjudication Committee.

Analysis Details: The same analytical approaches will be applied as for the primary efficacy analysis, including a primary analysis on the mITT Cohort and a sensitivity analysis on the Sensitivity Cohort.

Duration of shedding

Objective: To test the efficacy of HCQ to shorten the duration of SARS-CoV-2 shedding among those with SARS-CoV-2 infection.

Outcome: SARS-CoV-2 viral shedding by PCR

Cohort(s): mITT Cohort

Definition of Endpoint: For this analysis, a positive PCR test is defined as one where both targets are identified or one target is identified with $Ct \leq 40$.

PCR tests not meeting these criteria will be referred to as negative. The endpoint will be defined as the number of days from the first positive test until virus is no longer detected (a negative test has been observed with no positive tests following). Censoring will be indicated if the participant is still shedding on day 14. Participants who have a COVID-19 related hospitalization or death will be assumed to shed through day 14 and would have their days of shedding censored as if they had been observed through day 14.

Analysis Details: We will use a Cox Proportional Hazards model with robust standard errors to estimate the hazard ratio and corresponding 95% confidence interval and Wald test statistic. Robust confidence intervals and p-values will be displayed. This analysis represents a subset selected post-randomization and therefore requires adjustment for confounders. Due to lack of known confounders early in the epidemic, we propose that the list of baseline descriptors be assessed individually for their association with the primary endpoint. Those associated univariably with $p < 0.10$ will be included in this analysis. A hazard ratio greater than 1 (treatment/control) indicates efficacy of the intervention in shortening shedding.

Prevention of COVID-19 diagnosis

Objective: To test the efficacy of HCQ to prevent incident COVID-19.

Outcome: PCR-confirmed COVID-19 diagnosis post start of HCQ therapy through Day 14

Cohort(s): ITT, mITT, Sensitivity, Seronegative, Infected

Definition of Endpoint: COVID-19 is defined as symptomatic disease based on the following criteria with virologic confirmation (RNA PCR Ct \leq 40):

- At least TWO of the following symptoms: Fever ($\geq 38^{\circ}\text{C}$), chills, rigors, myalgia, headache, sore throat, new olfactory and taste disorder(s), OR
- At least ONE of the following symptoms: cough, shortness of breath or difficulty breathing, OR
- Severe respiratory illness with at least 1 of the following:
 - Clinical or radiological evidence of pneumonia, OR
 - Acute respiratory distress syndrome (ARDS)

A participant will be defined as having reached the endpoint if they have the diagnosis above. The time of the endpoint will be the onset of symptoms. Participants who do not have the endpoint will be censored at the last time they were known to be symptom-free. Death and hospitalization will be counted in the endpoint.

Analysis Details: We will use a Cox Proportional Hazards model with robust standard errors to estimate the hazard ratio and corresponding 95% confidence interval and Wald test statistic. Efficacy will be calculated as 1 minus the hazard calculated from the treatment coefficient. Robust confidence intervals and p-values will be displayed. The following baseline variables will be included to increase precision: presence of metabolic disease (if present in at least 10% of the population), weight, sex, age, and type of contact.

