Packaging and Labeling	The medication for home delivery will be dispensed in an unmarked container with the study label. The container will be labeled with a unique identifier. The container will be packed in a standard box used for mail delivery of medications as needed.	
Manufacturer	To be determined	To be determined

7.2. *Risks to the Participants*

7.2.1. *Risks Associated with PEP Administration with HCQ*

The risks associated with PEP reflect the adverse events (AEs) related to HCQ administration. With tens of millions of doses administered for malaria and autoimmune diseases, the side effect profile of HCQ is well described and the drug is generally well tolerated. With short-term administration (as opposed to chronic/year-long use in rheumatologic disease management), the major AEs are gastrointestinal (nausea, vomiting, dyspepsia, abdominal cramps, and diarrhea) and transient skin rashes. The gastrointestinal symptoms may vary by specific generic manufacturer of HCQ [35] and are best managed by taking the drug with food or a glass of milk (Appendix 6). A transient rash, most commonly morbilliform or psoriasiform, can develop in 10% of participants, often with a sustained loading dose, and is often managed by lowering the dose. To avoid this potential side effect, this protocol is using a short loading dose, not a sustained one. Uncommonly, idiosyncratic leukopenia/thrombocytopenia can occur and the drug

should not be given to those with underlying bone marrow disorders. Lastly, hypoglycemia can occur and those taking insulin or glucose-lowering drugs are at risk; blood glucose should be monitored.

Minor blurry vision may occur with acute HCQ use, is reversible, dose-related, and is generally not severe. It may also be associated with mild headaches. It is caused by deposition of HCQ in the cornea or ocular muscle weakness, and is not a predictor of long-term toxicity. Participants experiencing minor blurry vision may adjust to it with counselling and reassurance that it is reversible and not progressive.

More severe rashes, including drug-related eosinophilia with systemic symptoms and Stevens-Johnson syndrome occur rarely.

Long-term manifestations of HCQ, including retinitis, renal and hepatic disease, and cardiomyopathy ([Appendix 4](#)), are not likely in this 2-week PEP exposure.

7.2.2. *Risks Associated with COVID-19 Surveillance and Quarantine*

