10.1. Efficacy Assessments

10.1.1. Mid-nasal Swab

Participants will collect daily mid-nasal swabs for the initial 14 days and again at the Exit Contact for viral detection.

Index case participants in the index case sub-study will submit their baseline nasal swab for SARS-CoV-2 testing by PCR.

Participants will receive a swab kit either via courier or mail, which includes a Quick Start Instruction Card, swabs, plastic tubes for swab collection, and a return box with affixed Category B UN3373 label, as required by IATA guidelines [36].

Participants will collect and store their nasal swabs in a box for return.

The used swabs will be collected by the courier or returned via the postal service.

Swabs will be subjected to RNA amplification and tested for SARS-CoV-2, as applicable.

10.1.2. *Participant Survey*

Participants will be asked to complete Surveys (Daily Survey and Exit Contact Survey) that will include questions about symptoms from both the drug regimen and virus infection, review of concomitant medications, and other pertinent topics include information on any symptoms that may be associated with COVID-19.

10.2. *Adverse Events*

AE information will only be collected on close contact participants. For information regarding AEs in index case participants see [Section 10.2.7](#).

Participants will be asked to complete Surveys (Daily Survey and Exit Contact Survey) that include information on any symptoms that they are experiencing. In addition, AE review by a staff member (via telephone, Telehealth, or text messaging) will be performed.

All AEs must be recorded on electronic case report forms (eCRFs) if any of the following criteria have been met:

- All AEs meeting SAE definition
- All AEs judged by participant or clinician to be associated with study medication

10.2.1. *Serious Adverse Events*

An SAE is defined as any untoward medical occurrence that:

- Results in death
- Is life-threatening
- Requires inpatient hospitalization or prolongation of existing hospitalization
- Results in persistent or significant disability/incapacity
- Is an important medical event that may not be immediately life-threatening or result in death or hospitalization but may jeopardize the patient or may require intervention to prevent one of the other outcomes listed in the definition above

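### The COVID-19 analysis censors non-cases by symptom status alone, which discards observed event-free time and biases the hazard ratio if lasting PCR-negative symptoms differ between arms

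*SAP*

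**What the plan says.** In SAP 7.1.2, Prevention of COVID-19 diagnosis, the outcome is "PCR-confirmed COVID-19 diagnosis post start of HCQ therapy through Day 14". The event has two parts: "COVID-19 is defined as symptomatic disease based on the following criteria with virologic confirmation". The listed symptoms include fever, chills, myalgia, headache, sore throat, cough and shortness of breath. For cases, "The time of the endpoint will be the onset of symptoms". For everyone else, "Participants who do not have the endpoint will be censored at the last time they were known to be symptom-free". The model is Cox with robust standard errors, applied in five cohorts.

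The primary infection analysis (SAP 7.1.1) uses a different rule: "Participants who do not reach the endpoint will have their follow-up censored at their last negative RNA test". The Day 28 infection analysis also censors at the last negative test.

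Swabs and surveys are collected daily on Days 1 to 14 (Protocol 2, Schedule of Activities). The surveys include "questions about symptoms from both the drug regimen and virus infection" (Protocol 10.1.2). On HCQ side effects, Protocol 7.2.1 states that "the major AEs are gastrointestinal (nausea, vomiting, dyspepsia, abdominal cramps, and diarrhea) and transient skin rashes". It gives 10% for a transient rash and mentions mild headache without a rate. Protocol 7.4 calls gastrointestinal disturbance common. Protocol 7.3.1 expects these effects to be transient and to remit by themselves.

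The SAP does not define symptom-free. It names no sensitivity analysis for this censoring rule: SAP 7.1.3 varies only the Ct threshold of the primary endpoint, alongside the cohort-based analysis of SAP 7.1.1.

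**The concern.** The event needs symptoms and PCR confirmation, but the censoring rule looks only at symptoms. Take two participants with the same lasting non-COVID symptom from Day 3, for example nausea. One develops confirmed COVID-19 on Day 10 and counts as at risk until then. The other stays PCR-negative to Day 14 and is censored around Day 3. Whether the days after Day 3 count depends on how the participant's follow-up turns out.

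In a Cox model this thins the risk sets while all events stay in. If the thinning is the same in both arms, it largely cancels in the hazard ratio. If one arm has more lasting PCR-negative symptoms, its estimated hazard is too high. The symptoms need not be related to COVID-19 risk for this to happen.

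An imbalance is plausible but not established. Dosing runs to Day 14, which is also the horizon of this endpoint, so drug symptoms could still be present when follow-up ends. Protocol 3.2.5 also concedes that symptom reporting may depend on which treatment participants believe they are taking, and taste is only partly masked (Protocol 7.6). At stake is the estimate for one secondary efficacy endpoint.

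**Working it through.** **Plan's own figure.** The SAP gives no size for this endpoint. Its design for the primary endpoint (SAP 2.4) is 93 events, a 10% control attack rate and a 50% reduction: 93 / ((0.10 + 0.05)/2) = 1240, as stated. I borrow 1240 participants and 10% as a frame only.

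**Inputs from the documents.** Horizon of 14 days, 1:1 allocation, Cox model, and the event and censoring rules above.

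**Assumed inputs, because the documents give none.** The share of non-cases in each arm whose non-COVID symptoms last to the end of follow-up (p_H on HCQ, p_C on control), and when those symptoms start.

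**Approximation.** Let f be the fraction of follow-up lost by a participant censored at symptom onset. With events unchanged and time at risk reduced, the hazard ratio is multiplied by about

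(1 − f·p_C) / (1 − f·p_H)

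- Onset on Days 1 to 4: mean 2.5, f = (14 − 2.5)/14 = 0.821.
- Onset on Days 1 to 13: mean 7, f = 7/14 = 0.5.

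Worked example, 15% against 5%, early onset: (1 − 0.821 × 0.05)/(1 − 0.821 × 0.15) = 0.959/0.877 = 1.09.

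**Simulation.** Exponential event times, 10% control risk, independent participants, unadjusted Cox model. Non-cases with lasting symptoms are censored at onset, and all others at their event or Day 14.

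| Lasting symptoms, HCQ / control | Formula, early onset | Simulated HR (true 1), early onset | Simulated HR (true 1), onset Days 1–13 | Simulated HR (true 0.5), early onset |
|---|---|---|---|---|
| 5% / 5% | 1.00 | 1.00 | 1.00 | 0.50 |
| 5% / 2% | 1.03 | 1.02 | 1.02 | 0.51 |
| 10% / 5% | 1.04 | 1.05 | 1.03 | 0.52 |
| 15% / 5% | 1.09 | 1.09 | 1.05 | 0.55 |
| 30% / 10% | 1.22 | 1.21 | 1.11 | 0.61 |

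A 5% control risk gives nearly the same hazard ratios. Censoring the same participants at Day 14 returns 1.00 and 0.50.

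**Size against sampling error.** With 1240 participants, 10% risk in both arms and no effect, about 124 events are expected, 62 per arm. SE(log HR) ≈ √(1/62 + 1/62) = 0.18. The shift at 15%/5% is ln 1.09 = 0.086, about 0.5 SE. At 10%/5% it is ln 1.05 = 0.049, about 0.3 SE.

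For a single two-sided 5% test with early onset at 15%/5%, the simulated chance of a false harm signal rises from 2.4% to 7.3%. Power at a true ratio of 0.5 falls from 91% to 81%. These two figures take 10% as the COVID-19 risk. SAP 2.4 gives 10% for infection, so symptomatic COVID-19 would have fewer events and the shift would be smaller relative to the standard error.

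**The case against.** Four points deserve weight.

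1. *Meaning of symptom-free.* The censoring sentence follows closely on the list of COVID-19 symptoms, so it may mean free of those symptoms. Nausea, diarrhea and rash would then not trigger censoring, and the drug-driven imbalance would rest mainly on headache. This is a fair reading, and it weakens the case for an imbalance between arms. It does not repair the rule: PCR-negative cough, sore throat or headache lasting to Day 14 would still remove valid follow-up from non-cases only.

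2. *Last, not first.* The rule uses the last symptom-free time, so symptoms that clear restore the follow-up. The protocol expects HCQ effects to be transient. A symptom-free Day 28 survey might also count, in which case effects that stop after dosing would cost nothing. This stands: only symptoms lasting to the end of follow-up matter.

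3. *Missing swabs.* Swabs are self-collected, and the SAP sets no window between symptoms and the confirming PCR. A symptomatic participant without later swabs is not known to be event-free, and stopping follow-up early is reasonable there. This also stands, but it does not cover participants with complete negative swabs.

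4. *Unknown size.* A reader might infer that the rule will bias the result against HCQ, and by 10% to 25%. The documents do not support that. They give no rate of lasting symptoms in either arm, and their only figure is 10% for a transient rash. Double-digit bias needs a large share of HCQ participants still symptomatic at the end, well above control.

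**Conclusion.** The rule is flawed as written, because it discards observed event-free time from non-cases and not from cases. This holds on either reading of symptom-free.

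Bias in the hazard ratio is conditional. It arises only if symptoms with negative PCR that last to the end of follow-up are more common in one arm, and it then runs against that arm. Under equal shares, or symptoms that resolve in time, there is essentially none.

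On assumed imbalances of 3 to 10 percentage points the hazard ratio moves by about 2% to 9%, for example from 0.50 to between 0.51 and 0.55. More than that needs larger imbalances. The calculation assumes independent participants and symptoms unrelated to infection risk. Household clustering would change the standard errors, not the direction.

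Only this secondary endpoint is affected. The primary analysis, its 93 events and the monitoring bounds do not use the rule. If the excess of symptoms is on HCQ, the error hides benefit or suggests harm. It does not create a false claim of efficacy.

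**What to change.** Replace the censoring sentence in SAP 7.1.2 with a rule to this effect:

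- Participants without the COVID-19 endpoint are censored at the last day, up to Day 14, on which survey and PCR results show that the definition is not met.
- Symptoms with a negative PCR do not end follow-up.
- Symptomatic participants whose later swabs are missing are censored at their last assessment that rules out the endpoint.

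Defining symptom-free alone would not be enough, because the follow-up of PCR-negative participants with listed symptoms would still be lost. Reporting, by arm, how many non-cases were symptomatic at their last survey would show whether the choice of rule mattered.

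The cost is a few lines of SAP text before database lock and a small change to the analysis program. The daily surveys and swabs already supply every date. Sample size, primary endpoint and interim monitoring are unchanged.
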